### iv. rTMS

The parietal target in Experiments 1 and 3 will be the region of the left PPC with the greatest connectivity with the left hippocampus derived from the baseline resting-state fMRI session, (similar to Wang et al. 2014). The left PPC was chosen because of its dense connections with the hippocampus (Cavada & Goldman-Racic, 1989; Mesulam et al., 1977).

The target in Experiments 2 and 4 will be the M1 area of maximal connectivity with the right striatum. M1 has extensive projections to the striatum (Parent & Hazrati, 1995), and these regions are functionally connected at rest (Di Martino et al., 2008).

rTMS targets will be marked in the participant's anatomical MRI volume and located with a frameless stereotaxic system. If any experiment, for any reason, fails to produce useful individual targets, a literature-based location for the parietal cortex (Wang, et al., 2014) or motor cortex will be used as our location of stimulation. To reduce the influence of diurnal variations in the responsiveness to neuroplasticity protocols (Sale, Ridding, & Nordstrom, 2008), we will make every effort to test subjects during the same time of day.

*20-Hz Stimulation (facilitation)* will be delivered at 100% of the motor evoked potential threshold and 20-Hz in trains lasting 2 s for 20 min with 28 second rests in-between trains (similar to Wang et al., 2014).

*Continuous Theta-Burst Stimulation (cTBS; inhibition)* will be delivered at 80% of active motor threshold for 40 seconds (similar to Huang et al., 2005). cTBS consists of 50-Hz triplets separated by 200ms.

*Control stimulation.* As a negative control, rTMS will be delivered to the vertex with the same delivery parameter values and neuronavigation. Wang and colleagues (2014) used vertex stimulation as a control condition and found no significant effects on rsFC or behavior. In addition, there is no evidence that vertex stimulation causes other changes in rsFC (Jung et al., 2016).

**Contingency for Experiments 3 and 4 if we are unable to inhibit each network.** Because targeted inhibition of the hippocampal and striatal network with cTBS has not been demonstrated, it is possible that cTBS may not yield the expected inhibitory effects in Experiments 3 and 4. Thus, we will examine the results from the first three subjects receiving active stimulation in Experiments 3 and 4 and if there is no clear decrease of FC in the targeted network, we will run a cohort of 3 subjects using 1-Hz rTMS. We will proceed with the stimulation type that demonstrates the most reliable inhibitory effect.

*1-Hz Stimulation.* Stimulation will be delivered at 115% of the motor evoked potential threshold at 1-Hz continuously for 16 minutes (similar to Chen et al., 1997).

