### 3. Subjects

**a. Description of study population**

We will study 104 healthy individuals (26 in each experiment). We are requesting up to 122 healthy volunteers as the accrual ceiling to account for dropouts and screening failures. Participants who are withdrawn or drop out from the study will be replaced. NIH employees who are not members of the BNU will be allowed to participate. Based on previous experience, our anticipated dropout rate is 15%.

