## 4. Study Design and Methods

### a. Study overview

This protocol will include four experiments, each using rTMS and MRI, in a between-subjects design (Table 1). Experiments 1 and 3 will use PPC rTMS. Experiments 2 and 4 will use M1 stimulation.

	Active Stimulation Type	Active Stimulation Site	Targeted Network
Experiment 1	Facilitatory (20-Hz)	PPC	Hippocampal
Experiment 2	Facilitatory (20-Hz)	M1	Striatal
Experiment 3	Inhibitory (cTBS or 1-Hz)	PPC	Hippocampal
Experiment 4	Inhibitory (cTBS or 1-Hz)	M1	Striatal

Table 1. Experiment Details. PPC = Posterior Parietal Cortex, M1 = Motor Cortex.

Table 2 shows the timeline of each experiment. Each study will include FC and memory testing at baseline, 24-hours after, and two weeks after three days of rTMS. The number of days of rTMS is based on pilot data where three days of stimulation produces significant enhancement of rsFC in the hippocampal network in five out of six individuals tested. Each participant will make a maximum of 6 visits to the lab (not including screening), for a maximum time commitment of 14 hours. The 24-hour follow-up will occur between 12 and 48 hours after the last stimulation session, and the 2-week follow-up will occur 14-21 days after baseline measurements. Scanning will occur in the NIH NMRF. All visits will be outpatient.

	Baseline Day	rTMS Sessions	Post Stimulation Day	2-week follow-up
Group 1	Baseline FC and Memory	Active Stimulation 3-sessions	FC and Memory Testing	FC and Memory Testing
Group 2	Baseline FC and Memory	Vertex Stimulation 3-sessions	FC and Memory Testing	FC and Memory Testing

Table 2. Timeline of each experiment.

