## **8. Subject Safety Monitoring**

A credentialed physician or nurse practitioner will be on site for all rTMS administration and immediately available. This is the standard of care in community and academic clinical and experimental rTMS centers, nationwide. Study staff will be trained in rTMS administration, rTMS safety, and the measurement of the motor evoked potential threshold and will have performed 10 measurements under supervision. Study staff will monitor individuals during participation and participants will be encouraged to tell experimenters of any discomfort. Any subject exhibiting distress or who wishes to stop the experiment for any reason will be allowed to stop. Participants may withdraw at any time. Data of those participants that have completed at least the first session of any experiment (i.e. both MRI scan and behavioral assessment) will be kept and analyzed. A researcher may end experimentation for the following reasons:

- Abnormal response to rTMS including the occurrence of a seizure, loss of consciousness, or the participant's unwillingness to continue or headache produced by rTMS.
- Withdrawal of consent and/or decision to terminate.
- The experiment will be ended if the participant is unwilling to continue due to pain, or frustration with the procedures

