## **9. Outcome Measures**

### **a. Primary outcome measures**

- Pre-to-Post rTMS differences in rsFC and tbFC within the targeted memory network.

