To confirm modulation of the striatal network, the average timeseries of the right striatum seed will be correlated with all other voxels with available data before and after stimulation. These data will be submitted to AFNI's 3dLME linear mixed effects function, which will be used to reveal potential areas of significant change in rsFC and tbFC.

ii. Secondary Aims

Secondary Aims

Behavioral data will be submitted to a 3 x 2 x 2 ANOVA using timepoint (Pre-stimulation, post-stimulation, and follow-up), group (M1 vs. Vertex), and learning type (procedural and declarative) as factors. A significant interaction ( $p < 0.05$ ) between time, group, and learning type will confirm network-dependent modulation of each memory type.

To confirm changes in FC, a similar analysis will be performed as Primary Aim 1, except that the timeseries of the left hippocampus seed will be used instead of the striatal seed.

*Interim Analysis for Experiments 3 and 4.* The data from 3 initial participants in Experiments 3 and 4 will be examined to confirm that cTBS is inhibiting our networks of interest. FC will be calculated within the targeted networks and analyzed by study investigators. If, in the opinion of the study team, inhibition of these networks is unreliable, a cohort of 3 subjects will be run and will receive 1-Hz stimulation instead. Following this cohort, the results will be compared between stimulation protocols and the study team will make an informed decision about whether to continue with cTBS or to switch to 1-Hz stimulation instead.

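### Experiments 3 and 4 choose cTBS or 1-Hz by judgement from cohorts of 3 on the primary outcome, and the ceiling of 122 has no room for a cohort that is set aside

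*Combined protocol and SAP*

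**What the plan says.** Section 4.d.iv (contingency for Experiments 3 and 4) concedes that inhibition of these networks by cTBS has not yet been shown. The first three active participants are therefore examined, and "if there is no clear decrease of FC in the targeted network, we will run a cohort of 3 subjects using 1-Hz rTMS". It then says: "We will proceed with the stimulation type that demonstrates the most reliable inhibitory effect".

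Section 10.a (interim analysis for Experiments 3 and 4) describes the same step in other terms: "If, in the opinion of the study team, inhibition of these networks is unreliable, a cohort of 3 subjects will be run". The team then compares the two protocols and decides whether to stay with cTBS or switch.

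Section 9.a gives the primary outcome as "Pre-to-Post rTMS differences in rsFC and tbFC within the targeted memory network". The look and the primary contrast therefore use the same kind of measurement.

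Section 3.a plans 104 participants (26 per experiment), an anticipated dropout of 15%, and a ceiling of 122 for dropouts and screening failures. On replacement it says: "Participants who are withdrawn or drop out from the study will be replaced". Section 10.b plans 13 analysable participants per group and derives 122 from attrition of about 15%. Neither section mentions the contingency cohorts.

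**The concern.** Three things are left open.

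- **The rule.** The trigger is a decrease that is not clear in one section and the team's opinion in the other. The final choice rests on reliability in one and on an informed judgement in the other. Neither says whether resting-state or task-based FC decides, gives a criterion, or says whether three means three per experiment or three across both.
- **The analysis set.** Nothing says whether the selected or the non-selected cohort counts toward the 13 active participants. As written, that would be settled after their primary-outcome data have been seen.
- **The count.** A participant who completes the study on the stimulation type that is not chosen has neither dropped out nor been withdrawn, so the replacement rule does not reach that cohort. If the ceiling is already used up by attrition, the planned 26 analysable per experiment cannot be met once a cohort is set aside.

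This affects two of the four primary aims (Aims 3 and 4). The contingency is the plan's own provision for a result it regards as possible.

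**Working it through.** **Inputs.** From sections 3.a and 10.b: 104 analysable, 13 per group, 15% dropout, ceiling 122. From sections 4.d.iv and 10.a: cohorts of 3.

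**Reproducing the ceiling.** 104/(1 - 0.15) = 122.35, which matches 122. In reverse, 122 × 0.85 = 103.7 completers. Attrition alone uses the whole margin of 122 - 104 = 18, before any screening failure.

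**Setting a cohort aside.** Whichever type is chosen, the three completers on the other type fall outside the primary contrast. The number set aside is 3 if three means in total, or if only one experiment uses the contingency. It is 6 if three means per experiment and both use it.

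| Set aside | Analysable at 122 and 15% dropout | Dropout at which 122 still suffices | Accrual needed at 15% |
|---|---|---|---|
| 0 | 103.7 | 1 - 104/122 = 14.8% | 104/0.85 = 122.35 |
| 3 | 103.7 - 3 = 100.7 | 1 - 107/122 = 12.3% | 107/0.85 = 125.9, so 126 |
| 6 | 103.7 - 6 = 97.7 | 1 - 110/122 = 9.8% | 110/0.85 = 129.4, so 130 |

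**Bias from keeping the selected three.** The plan gives no criterion, so cut-offs must be assumed. The illustration uses one FC change score with unit SD and no true effect of either type. cTBS is kept if the mean fall in its three exceeds a cut-off. Otherwise a 1-Hz cohort of three is run and the cohort with the larger fall is kept. Ten new active participants are added and compared with 13 vertex participants by a two-sample t-test (1,000,000 simulated trials per cut-off).

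| Cut-off (SD) | Shift (SD) | Rejection toward inhibition (nominal 2.5%) | Two-sided rejection |
|---|---|---|---|
| 0 | -0.064 | 3.38% | 4.90% |
| 0.375 | -0.073 | 3.55% | 4.97% |
| 0.75 | -0.075 | 3.53% | 4.93% |

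The standard error of the difference is √(2/13) = 0.392 SD.

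A hand check is available for the extreme rule that always runs both cohorts and keeps the lower mean. The expected lower of two means of 3 is -(1/√3)(1/√π) = -0.577 × 0.564 = -0.326 SD. Diluted over 13 this is -0.326 × 3/13 = -0.075 SD, in line with the simulation. When the selected three are replaced by three new participants, the shift vanishes and rejection toward inhibition returns to about 2.5%.

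**The case against.** The best defence is that this is a sensible early check and that its ordinary path needs no change. Section 4.d.iv calls the cTBS three the first active participants of these experiments, and section 10.a speaks of continuing with cTBS, so they look like regular participants who count if cTBS passes. On that path 104 and 122 are consistent. The time point is also not truly open: the pre-to-post wording of the outcome is most naturally read as baseline to the post-stimulation day. The 15% is approximate, and section 4.b.i counts someone who misses only the two-week visit as complete. The bias from the selected three is small. All of this stands. It makes the shortfall conditional, but it does not supply the missing rule, the fate of the cohorts or the count when the contingency is used.

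A reader might infer more than the documents support:

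- **That both cohorts are to be pooled.** Section 8 keeps and analyses "Data of those participants that have completed at least the first session of any experiment". That sentence directly follows the statement that participants may withdraw, and it concerns people who leave early. It does not address stimulation type or the primary contrast.
- **That vertex participants given the abandoned parameters must be excluded.** Section 4.d.iv says "rTMS will be delivered to the vertex with the same delivery parameter values and neuronavigation", so a switch could leave controls whose parameters differ from the active arm. The same section gives grounds for treating vertex stimulation as inert, so pooling them is arguable.
- **That the error rate of a choice at n = 3 can be quantified.** This would need a criterion and an effect size for cTBS or 1-Hz. The documents give neither; the only pilot effect comes from 20-Hz hippocampal stimulation.
- **That the primary test is seriously inflated.** Two-sided error stays near 5%.

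**Conclusion.** The concern holds as a conditional fault in the count and an undefined analysis set. The figure of 122 is wrong as written for the contingency path: at the stated 15% dropout it delivers about 101 analysable participants if 3 are set aside, or about 98 if 6 are, against 104 planned. It absorbs them only if dropout is at most 12.3% or 9.8%, with no screening failures charged to it. If cTBS passes the first look and its three are kept, nothing in the count needs changing.

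Selection bias is a minor component: 0.06-0.08 SD toward inhibition against a standard error of 0.39, with rejection in that direction about 3.5% instead of 2.5%. Those figures rest on assumed cut-offs, a single normally distributed FC score and no true effect. The planned voxelwise mixed model was not simulated. The counts rest only on the plan's own numbers and on the set-aside participants being completers.

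**What to change.** 1. Reconcile sections 4.d.iv and 10.a into one rule fixed before the first look. It should name the FC measure and the criterion, and say whether three is per experiment or in total.
2. State that the non-selected cohort does not enter the primary contrast. Report the primary result with and without the selected three. As a sensitivity analysis only, also report it with and without any vertex participants given the abandoned parameters.
3. In sections 3.a and 10.b, state that 122 covers attrition only, and give the analysable number if the contingency is used (about 101 or 98).

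The cost is protocol wording, a small amount of extra analysis and a slightly less favourable stated count. No extra enrolment is required. If the sponsor would rather raise the ceiling, the figures are 126 or 130, that is 4 or 8 more people under a procedure that section 7.b rates above minimal risk. Which stimulation type to use remains the sponsor's decision.

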#### v. Cognitive Battery

The purpose of the battery is to detect effects on other memory processes other than those targeted in the study, characterize participants cognitive abilities at baseline, and to monitor for unexpected deleterious effects of stimulation. The data will be treated as exploratory. Some tasks will only be included at baseline (indicated below). These tests will not be given inside of the scanner. The battery includes the following tests:

- 1) Flanker Inhibitory Control and Attention Test (executive function and attention) - Participants respond to the direction of a target arrow while inhibiting attention to arrows flanking the target arrow (~3 minutes). This test will only be given at baseline.
- 2) Dimensional Change Card Sort Test (executive function and set-shifting) – Participants must match pictures based on one of two rules. These rules are transposed and participants' set-shifting abilities are measured by their accuracy and reaction time (~4 minutes). This test will only be given at baseline.
- 3) List Sorting Working Memory Test (for working memory) – Participants are given two lists of items (e.g. animals and foods) and are asked to list the items in size order. The task requires the

participant to concurrently remember the items while sorting (< 10 minutes). This test will only be given at baseline.

- 4) Picture Sequence Memory Test (for story sequence memory) – Participants are given a list of objects and must remember the order of these objects in relation to each other. For example, if object A is listed in position X, the participant must recall what object is in position X+1 (~7 minutes).
- 5) Oral Reading Recognition Test (for language) – The participant is asked to read individual words and the researcher records whether the word is read correctly (~3 minutes). This test will only be given at baseline.
- 6) The Picture Vocabulary Test (for language) – Participants are aurally presented with a word and must match that word with one of four pictures that best represents the meaning of the word. The number of correct responses is recorded (~4 minutes). This test will only be given at baseline.
- 7) Pattern Comparison Processing Speed Test (for processing speed) – Participants are presented with two pictures and must determine whether they are the same or different. The number of correct responses in 90 seconds is recorded (~3 minutes). This test will only be given at baseline.
- 8) Georgia Complex Figures task (for visual memory) – Participants are asked to copy a complex drawing, and reproduce it from memory after a 20-minute delay. The number of successful elements of the complex figure are recorded (~ 5 minutes without delay).
- 9) Category Fluency test (for category fluency) – Participants are given a category (e.g. animals, tools) and are asked to name as many category members in 60 seconds as possible (~ 2 minutes).
- 10) Verbal paired associates test (for verbal memory) – This test is similar to the WPT-O, but instead of new items used at each time point, the same pairs are retested at the end of the week of stimulation (~ 5 minutes).
- 11) Everyday Memory Questionnaire (EMQ) (a subjective memory assessment) – Participants are asked 13 questions to assess their impression of their memory function. For each question, participants rate how often a particular memory problem has occurred, e.g. not being able to recall a word, having to check something that has already been done (~ 3 minutes).
- 12) Neuro-QOL forms: Depression, Fatigue, Sleep Disturbance – Participants report outcome measures through computer adaptive tests (CAT), short forms, or scales. (~ 20 minutes).

#### vi. Amsterdam Resting-State Questionnaire

The ARSQ will be administered immediately after each resting-state scan and includes 50 questions related to patterns of mentation that could occur during resting-state scanning (see Appendix C). For each question, the participant is asked whether they agree or disagree with a statement related to their thoughts in the scanner. This questionnaire generally takes < 8 minutes to complete.

All clinical rating scales can be performed using an interpreter in any language. Interpreters will also be available for other protocol procedures as necessary.

#### e. End of participation

Volunteers will remain under the care of their own providers. No care will be offered to those participating in this protocol, except for any acute care required for adverse events. Findings of clinical significance, e.g., significant pathology on MRI will be shared with participants and any provider whom they designate.

## 5. Management of Data and Samples

### a. Storage

The results of testing will be stored on password-protected computers or backed up on media stored in locked cabinets. Keys to participant identity will be stored in lab notebooks, available only to study investigators. Samples will not be stored under this protocol.

### b. Data

This protocol is not subject to the Genomic Data Sharing (GDS) policy. Data may also be shared with collaborating laboratories at NIH or outside of NIH and/or submitted to NIH-designated repositories and databases if consent for sharing was obtained

Data will be stripped of identifiers and may be coded (“de-identified”) or unlinked from an identifying code (“anonymized”). When coded data is shared, the key to the code will not be provided to collaborators, but will remain at NIH. Data may be shared with investigators and institutions with an FWA or operating under the Declaration of Helsinki (DoH) and reported at the time of continuing review. Sharing with investigators without an FWA or not operating under the DoH will be submitted for prospective IRB approval. Submissions to NIH-sponsored or supported databases and repositories will be reported at the time of Continuing Review. Submission to non-NIH sponsored or supported databases and repositories will be submitted for prospective IRB approval.

## 6. Additional Considerations

### a. Research with investigational drugs or devices

- Magnetic resonance imaging system operating in research mode
- Magstim Rapid Therapy System and the
- Magstim Air Film Coil

According to 21 CFR 812.3 (m) and FDA “Information Sheet Guidance for IRBs, Clinical Investigators, and Sponsors: Significant Risk and Nonsignificant Risk and Nonsignificant Risk Medical Device Studies January 2006 (accessible at <http://www.fda.gov/downloads/RegulatoryInformation/Guidances/UCM126418.pdf>), the use of these devices in the study are a Non-significant Risk study. 21 CFR 812.3(m) enumerates four criteria for a Significant Risk Device Study; none of these apply to this study:

1. is intended as an implant and presents a potential for serious risk to the health, safety, or welfare of a subject;  
*None of the three devices are implants.*
2. is purported or represented to be for a use in supporting or sustaining human life and presents a potential for serious risk to the health, safety, or welfare of a subject;  
*None of the three devices are for use in supporting or sustaining human life.*
3. is for a use of substantial importance in diagnosing, curing, mitigating, or treating disease, or otherwise preventing impairment of human health and presents a potential for serious risk to the health, safety, or welfare of a subject; or

*The investigational use of the three devices is not of substantial importance in diagnosing, curing, mitigating, or treating disease, or otherwise preventing impairment of human health.*

4. otherwise presents a potential for serious risk to the health, safety or welfare of a subject  
*The use of the legally marketed MRI system in research mode will be performed under operating conditions below each of the limits (field strength, Specific Absorption Rate, time rate of change of gradient fields and sound pressure levels) deemed to be significant risk by the FDA as stated in the FDA guidance document, Criteria for Significant Risk Investigations of Magnetic Resonance Diagnostic Devices.*

*The Magstim Rapid2 Therapy System is legally marketed, indicated for “the treatment of Major Depressive Disorder in adult patients who have failed to achieve satisfactory improvement from prior antidepressant medication in the current episode.” The Magstim Air Film Coil is legally marketed as “a stimulating coil solely intended for use with the Magstim® Rapid2 Stimulating Unit for the purposes of peripheral nerve stimulation. The Air Film Coil is an accessory of the Magstim® Rapid2 Unit.” Both are used in combination in rTMS. Their use in this study is not within the labeled indications. The major risk of rTMS and cTMS is the risk of seizure. Brief, self-limited, seizures were seen in early studies, before limits were established for combinations of delivery parameters. However, this risk has been reduced to the order of one in every 50,000 sessions. For rTMS, safety guidelines have been developed (Wassermann, 1998) and updated (Rossi, Hallett, Rossini, & Pascual-Leone, 2009). These guidelines were incorporated into FDA’s Class II Special Controls Guidance Document: Repetitive Transcranial Magnetic Stimulation (rTMS) Systems in Table 2. Maximum Safe Train Duration (seconds) Limits for Avoiding Seizures. The rTMS and 1-Hz Stimulation in this study are below the limits defined in these documents. Furthermore, the study subjects are a lower risk since subjects with any neurological or psychiatric disorders, history of seizure or taking certain medications are excluded. cTBS was not included in the guidelines. However, there is only a single report of seizure with cTBS (Lerner, Wassermann, & Tamir, 2019; Oberman et al., 2011, Rossi et al., submitted manuscript). In that single patient, the study was conducted in at stimulation intensity levels higher than in this study. Over the past 20 years, the FDA has generally waived pre-IDE inquiries for TMS/rTMS studies on an NSR device basis.*

*All subjects will wear hearing protection.*

The protocol will comply with the abbreviated IDE requirements under 21 CFR 812.2(b), available at:  
<https://www.accessdata.fda.gov/scripts/cdrh/cfdocs/cfCFR/CFRSearch.cfm?fr=812.2>

